3.1 Background

In patients with insulin dependent diabetes mellitus, glycemic control is influenced by numerous factors, such as insulin dosage, insulin absorption, timing, physiological/lifestyle factors such as exercise, food intake, sleep, hormones and illness. These factors may contribute to significant variability in insulin requirements, which makes self-management of diabetes challenging.

Today, there are 55 million patients globally taking insulin through injections as compared to the 1 million administering insulin via pump therapy. Some of these patients will move to insulin pump therapy over the course of their lifetime, but the majority will continue using injections. Their rationale to continue with insulin injections include the following reasons:

- There is higher patient out-of-pocket cost associated with pump therapy;
- The physical experience of wearing a pump device is not appealing; and
- There has been growth in new therapy options available to injection users, such as CGM, smart pens, and decision support apps.^[1]

While CGM has greatly improved a patient's ability to get rapid and accurate glucose readings, patients are still required to make hundreds of decisions a day with little guidance on what to eat, what to dose, when to dose, and how to manage activities such as exercise. Without actionable therapy guidance, the following key needs remain unmet for these patients:

- Understanding how specific foods, physical activity, sleep patterns, and other routines affect their personal glucose levels;
- Recovering quickly from low and high glucose levels;
- Avoiding overnight lows;
- Optimizing physical exercise to stay in range; and
- Knowing exactly how much insulin to take, and when, at mealtime and throughout the day.^[2]

Due to the lack of guidance on the key needs listed above, multiple daily injections (MDI) patients on the current state of the art therapies spend an average of 45-51% of their time within a healthy glycemic range, known as Time in Range (TIR)^[3], which is well below the TIR outcomes for pump users^[4, 5]. The overall goal of the Smart CGM system is to significantly improve TIR and quality of life (QOL) for injection-based insulin users by improving the user experience in three key areas:

- (1) Personalizing dosing recommendations that are tailored to the patient's own physiology, lifestyle, and diabetes state;
- (2) Providing holistic decision support to the user in point-of-care situations; and,

Medtronic Business Restricted

(3) Reducing the burden of logging information relevant to diabetes management.

The Smart CGM system will accomplish this by providing the patient with intelligent automation, detection, insights, and recommendations that will enable them to achieve significantly improved TIR and QOL as an MDI user.

3.2 Purpose

The purpose of this study is to collect sensor, insulin, sleep, activity and food/meal data for a minimum of 90 days of wear (Phase 1) and up to a maximum of 9 months of device wear (Phase 2) with optional insulin injection video capture and/or menstrual cycle tracking and/or cardiac monitoring in subjects with insulin requiring diabetes 2-80 years of age.

4 Objectives and/or Endpoints

4.1 Objectives

4.1.1 Primary Objective(s)

The primary objective of this feasibility study is to collect data to be used for development of Medtronic Diabetes and Cardiac Diagnostics devices and products.

4.2 Endpoints

Descriptive statistics will be performed; no statistically powered analyses or hypothesis testing will be performed.

- Glycemic control: Percentage of Time in Range (SG <70 mg/dL, 70-180 mg/dL, and >180 mg/dL)

4.2.1 Other Descriptive Endpoints

- Summary of completed data collection/available data
- Summary of study questionnaire results

4.3 Safety

Descriptive summary will be used to characterize safety events:

Medtronic Business Restricted

- Serious adverse events (SAE)
- Device related AEs
- Procedure related AEs
- Serious adverse device effect (SADE)
- Unanticipated adverse device effect (UADE)
- Severe hypoglycemia
- Diabetic ketoacidosis (DKA)

4.4 Device Deficiencies

Descriptive summary will be used to characterize device deficiencies.

5 Study Design

The study is a multi-center, prospective single-arm design without controls. All subjects will participate for a minimum of 90 days (Phase 1) and some subjects 18 years of age or older will participate for up to 9 months (Phase 2). All subjects will wear the Guardian Connect system (real-time CGM) continuously and use smart insulin pens or insulin pens with smart caps for multiple daily injections and continue their standard therapy throughout the duration of the study.

Once trained, each subject 14 years of age or older or their parent or guardian (if applicable) may insert a sensor in the abdomen or arm. Subjects 2-13 years of age or their parent or guardian may insert a sensor in the abdomen or buttocks.

Only subjects 13 years of age and older will wear an Apple Watch (waking hours), a Fitbit (sleeping hours) and have the Klue app.

The subject's insulin delivery, sleep, physical activity (as applicable), food intake data, and medication (as applicable) will be collected through applications with meal logging and medication requiring manual entry. In addition, subjects may also participate in optional self-administered insulin injection video capture and upload using a secure cloud-based site and/or monthly menstrual cycle logging using Apple Health and/or cardiac monitoring using BodyGuardian MINI.

Only subjects 13 years of age and older who choose to participate in optional video capturing of self-administered insulin injection will use the Klue app on the sponsor-provided smartphone to record insulin injections (capturing two videos per each injection location) any time during the study, and upload videos to a secure cloud-based site on the sponsor-provided smartphone. All other app data will be sent automatically to the cloud throughout study participation. Subjects will also be asked to enable location services on the sponsor-provided smartphone throughout the study.

Only subjects weighing more than 10 kg who choose to participate in optional cardiac monitoring using

Medtronic Business Restricted

the BodyGuardian MINI monitor, should wear the monitor for a minimum of 14 days.

Electronic device data will be collected from the study devices using CareLink Personal and the FoodPrint mobile app and Nutriño cloud. Each site should create a new CareLink Professional account to review subjects' CGM data. CareLink software uses TLS technology, which encrypts all data it stores (21 CFR Part 11 compliant). Wearables will be reset to factory settings at subject's end of study visit. Sponsor-provided smartphone and watch will be reset to factory settings after subject exits study and prior to device return to sponsor.

Throughout the study, both in Phase 1 and Phase 2, subjects will continually use the Guardian Connect system, track insulin delivery via the smart pen or pen caps, track sleep, track activity, and respond to prompts (as applicable). Subjects are instructed to use information from the Guardian Connect app in an adjunctive manner, per product labeling. The general study timeline of activities is as follows:

Phase 1

- Day 1-30

For 7 consecutive days during Days 8-27 (to ensure there is sufficient time for site to review surveillance report prior to Visit 4), each subject should log food consumption (meals, drinks and snacks) concurrent with CGM, sleep and activity tracking, and insulin delivery data collection. The subject is required to check a fasting SMBG using the study meter after a minimum of 8 hours of fasting for two mornings during the week they log their food.

- Day 31-90

Each subject should log food consumption for a minimum of 7 consecutive days per month.

Day 100 will be the EOS unless the subject is participating in Phase 2. If EOS, devices should be returned, wearables reset to factory settings, and subject's participation in the study will be completed.

Phase 2

- Day 91-280

Some subjects 18 years of age or older will continue to provide data for an additional 180 days based on adherence to study requirements demonstrated during Phase 1. Subject will be asked to log food consumption (meals, drinks and snacks) for a minimum of 7 consecutive days per month concurrent with CGM, sleep and activity tracking, and insulin delivery data collection. At End of Study (EOS, Day 280 (± 7 days)) devices should be returned, wearables reset to factory settings, and subject's participation in the study will be completed.

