Study Design	
The study is a multi-center, prospective single-arm design without controls. All subjects will participate for a minimum of 90 days (Phase 1) and some subjects 18 years of age or older will participate for up to 9 months (Phase 2). All subjects will wear the Guardian Connect system (real-time continuous glucose monitoring (CGM)) continuously and use smart insulin pens or insulin pens with smart caps for multiple daily injections and continue their standard therapy throughout the duration of the study.
 
Once trained, each subject 14 years of age or older or their parent or guardian (if applicable) may insert a sensor in the abdomen or arm. Subjects 2-13 years of age or their parent or guardian may insert a sensor in the abdomen or buttocks.
 
Only subjects 13 years of age and older will wear an Apple Watch (waking hours), a Fitbit (sleeping hours) and have the Klue app.
 
The subject's insulin delivery, sleep, physical activity (as applicable), food intake data, and medication (as applicable) will be collected through applications with meal logging and medication requiring manual entry. In addition, subjects may also participate in optional self-administered insulin injection video capture and upload using BOX and/or monthly menstrual cycle logging using Apple Health and/or cardiac monitoring using BodyGuardian MINI.
 
Only subjects 13 years of age and older who choose to participate in optional video capturing of self-administered insulin injection will use the Klue app on the sponsor-provided smartphone to record insulin injection (capturing two videos per each injection location) any time during the study, and upload videos to BOX on the sponsor-provided smartphone. All other app data will be sent automatically to the cloud throughout study participation. Subjects will also be asked to enable location services on sponsor-provided smartphone throughout the study.
 
Only subjects weighing more than 10 kg who choose to participate in optional cardiac monitoring using BodyGuardian MINI should wear the monitor for a minimum of 14 days.
 
Electronic device data will be collected from the study devices using CareLink Personal software and the FoodPrint app and Nutrino cloud. Each site should create a new CareLink Professional account to review subjects' CGM data. CareLink software uses TLS technology, which encrypts all data it stores (21 CFR Part 11 compliant). Wearables will be reset to factory settings at subject's end of study visit. Sponsor-provided smartphone will be reset to factory settings prior to device return to sponsor.
 
Throughout the study, both in Phase 1 and Phase 2, subjects will continually

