
Medtronic Business Restricted

	
use the Guardian Connect system, track insulin delivery via the smart pen or pen caps, track sleep, track activity, and respond to prompts (as applicable). Subjects are instructed to use information from the Guardian Connect app in an adjunctive manner, per product labeling. The general study timeline of activities is as follows:
 
Phase 1
 
▪ Day 1-30 
For 7 consecutive days during Days 8-27 (to ensure there is sufficient time for site to review surveillance report prior to Visit 4), each subject should log food consumption (meals, drinks and snacks) concurrent with CGM, sleep and activity tracking, insulin delivery data collection, and medication. The subject will be asked to check a fasting SMBG using the study meter after a minimum of 8 hours of fasting for two mornings during the week they log their food.
 
▪ Day 31-90 
Each subject should log food consumption for a minimum of 7 consecutive days per month.
 
Day 100 will be the End of Study (EOS) unless the subject is participating in Phase 2. If EOS, devices should be returned, wearables reset to factory settings, and subject's participation in the study will be completed.
 
Phase 2
 
▪ Day 91-280 
Some subjects 18 years of age or older will continue to provide data for an additional 180 days based on adherence to study requirements demonstrated during Phase 1. Subjects will be asked to log food consumption (meals, drinks and snacks) for a minimum of 7 consecutive days per month concurrent with CGM, sleep and activity tracking, insulin delivery data collection, and medication. At End of Study (EOS, Day 280 (± 7 Days)) devices should be returned, wearables reset to factory settings and subject's participation in the study will be completed.

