6.2.1 Insulin capture devices and associated apps

6.2.1.1 InPen Basal smart cap

The InPen Basal smart cap , also referred to as InCap, is a reusable electronic pen injector cap for single-patient use by people with diabetes. The Cap is compatible with Levemir®, Tresiba®, Lantus®, Basaglar®, and Toujeo® prefilled pens. In this study, the smart cap should be used under the supervision of an adult caregiver or by a patient age 7 and older for the tracking of long-acting insulin doses.

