6.4.2 Insulin capture devices and associated apps (type, time, date, amount)

6.4.2.1 Companion Medical InPen for use with Humalog, NovoLog, Fiasp U100 (rapid-acting only)

Companion Medical InPen smart insulin pen system that combines a reusable, Bluetooth® insulin pen and an intuitive mobile app that helps users take insulin doses. In this study, the InPen pen and InPen Diabetes Management app should be used under the supervision of an adult caregiver or by a subject age 7 and older for the self-injection of a desired dose of insulin.

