7.3 Inclusion Criteria

1. Individual is 2-80 years of age at time of consent.
2. A clinical diagnosis of type 1 or type 2 diabetes as determined by investigator for:
 - o at least the last 6 months for subjects 2-6 years of age
 - o at least the last 12 months for subjects 7-80 years of age
3. Subject is on multiple daily injection therapy (3 or more insulin injections per day one of which is a long acting insulin injection), is currently using or is willing and can afford to use insulin pen(s) and pen cartridge(s).
4. Subject is currently using or is willing to use the Guardian Connect system during the study.
5. Subject agrees to comply with the study protocol requirements.
6. For adult subjects: Subject is capable of providing legal consent without a legal authorized representative.

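### Does the *or* between smart pen and smart cap leave one insulin class unrecorded and uncounted?

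*Protocol*

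**What the plan says.** Protocol Section 5 states that all subjects "use smart insulin pens or insulin pens with smart caps for multiple daily injections and continue their standard therapy"; the Synopsis and SAP Section 5 use the same phrase. The ongoing instruction, in the Synopsis and Section 5, is to "track insulin delivery via the smart pen or pen caps".

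Each device serves one insulin class. Section 6.4.2.1 restricts the InPen to three named rapid-acting insulins. Section 6.2.1.1 provides the smart cap "for the tracking of long-acting insulin doses", and Section 6.2.1.3 lists the long-acting pens that the adapters fit. Inclusion criterion 3 (Section 7.3) requires "3 or more insulin injections per day one of which is a long acting insulin injection", together with use of, or willingness to use, insulin pens and cartridges.

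The visit table (Section 9.2) collects diabetes therapy at Visit 1, with insulin and dosing regimen among the examples, and dispenses insulin capture devices at Visit 2. Section 6.6.3 logs each subject's devices on an eCRF. The reporting commitment in Protocol Section 13.7 and SAP Section 7.9.2 is a single line summarising completed and available data, with no split by data stream or insulin class.

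**The concern.** A full automatic insulin record needs both devices, yet no sentence says that each subject must have both. The entry criteria do not ask whether a subject's insulins fit the devices, and completion is not tied to insulin capture. A subject with only one class recorded could therefore count towards the 260 completers, and the report need not show it.

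This would matter because data collection is the primary objective and insulin is one of the five streams named in the purpose (Section 3.2). A dose not recorded during the study cannot be recovered afterwards. FoodPrint can log insulin by hand (Section 6.4.4), but the training row in Section 9.2 covers only meals and medication.

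**Working it through.** **The plan's own figure.** The Synopsis gives at least 260 completers from up to 500 enrolled: 260 / 500 = 52%. No precision, power or dropout calculation lies behind it, so there is nothing further to reproduce. The 260 is defined by completing 90 days of data collection (in Section 7.1, about 100 days of participation), not by having insulin records.

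**What one device would miss.** Inputs: 3 injections a day, one long-acting (Section 7.3); 90 days in Phase 1 and 180 more in Phase 2 (Section 5). Assumption: the other two daily doses are listed rapid-acting insulins.

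| Period | All injections | Pen only, at most | Cap only, at most |
|---|---|---|---|
| Phase 1, 90 days | 3 × 90 = 270 | 2 × 90 = 180 (67%) | 1 × 90 = 90 (33%) |
| Both phases, 270 days | 3 × 270 = 810 | 2 × 270 = 540 | 1 × 270 = 270 |

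The loss per affected subject would be large. The number affected is not in the documents. If a share f of 260 completers lacked one class, 260 × (1 − f) would have both: 247 at 5%, 234 at 10%, 208 at 20%. These shares are assumptions; nothing in the documents supports any of them over zero.

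**Is the one-device reading intended?**

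- The devices are to serve multiple daily injections. Since each covers one class, the phrase describes such a regimen only if pen and capped pen are alternatives for a given dose.
- In Section 9.2 the row for dispensing insulin capture devices is plural and has an unqualified mark at Visit 2. The Apple Watch, Fitbit and cardiac monitor rows are marked *if applicable*. The protocol flags optional devices, and these are not flagged.
- Criterion 3 speaks of pens and cartridges for a regimen that must include a long-acting insulin.

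**Would a gap be noticed?** Insulin tracking is a named topic when sites discuss the sponsor's surveillance reports at Visits 3, 4 and 5 and Phase 2 Visits 6 to 11 (Sections 9.1.1 and 9.2). Visit 3 is at Day 10 ± 4. If a missing long-acting record were seen then, about 6 to 14 doses would be lost rather than 90. This assumes the report is available and shows the gap; the protocol promises reports only as available and does not say they are split by class.

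**Can capture by class be derived?** Yes. Therapy is recorded at Visit 1, devices are logged per subject, and the heading of Section 6.4.2 lists insulin type, time, date and amount as captured fields. Because each device serves one class, its records identify the class.

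**Would rewording or a new metric gain anything?** Replacing *or* with *and* recovers no doses for a subject whose insulin is not on a device list, because standard therapy continues. A count of days with at least one recorded dose would not show completeness either: one of two rapid-acting doses recorded each day gives 90 of 90 days but only 90 of 180 doses.

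**The case for a change.** The strongest case for a change is that the one-device reading is not fanciful. Section 6.4.2.2 describes app version 5.4.4 as taking data from the InPen alone, while Section 6.2.1.2 describes version 6.0.0 as taking data from the InPen or the cap. The protocol does not say which subjects receive which version. Phase 2 entry depends on adherence to study requirements, and failing a requirement is a ground for withdrawal (Section 9.10), so a site might not know whether a one-device subject is adherent. With data collection as the objective, a clarifying phrase and a few table rows would cost little.

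Part of this stands. No sentence requires both devices, device fit is not a named item at Visit 1, and a breakdown by class is not specified. User guides supplied under separate cover (Section 17.2) may address fit, but cannot be checked here.

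The rest is weaker. Capture itself could not be recorded at Visit 1, because devices are dispensed at Visit 2. Unspecified reporting is not the same as no reporting: a summary of available data can include insulin by class. Sleep, activity and food have no stream-level specification either, so insulin is not treated worse than they are.

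**Conclusion.** The concern identifies loose wording and an unspecified breakdown, not a fault that requires a change. The natural reading is dose by dose: the pen for rapid-acting insulin, the cap for long-acting insulin. A competent analyst summarising available data would tabulate who had both classes, one or neither, state the day threshold used and keep Phase 1 and Phase 2 denominators apart. The planned data allow this.

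Followed as written, the plan gives sound glucose, safety and data-availability summaries, and no stated figure is wrong. There is no hypothesis test and no insulin endpoint; the time-in-range endpoint uses sensor glucose only. For any one-device subject the possible loss is 90 or 180 of 270 Phase 1 injections, but the number of such subjects is unknown and may be zero. The conclusion assumes that sites dispense both devices where a subject's insulins fit them, and that insulin-tracking reviews are held as scheduled.

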5.1 Duration

The study is anticipated to last approximately 24 months from first investigational center initiation to finalization of all data entry and monitoring procedures. Subject participation is expected to be

Medtronic Business Restricted

approximately 100 days and approximately 280 days for some adult subjects participating in Phase 2.

5.2 Rationale

This study is intended to allow collection of sensor, insulin, activity and food/meal data for use in the development of Medtronic Diabetes and Cardiac devices and products.

6 Product Description

6.1 Intended Population

A diverse population of type 1 or type 2 insulin-requiring subjects who use multiple-daily injections (MDI) insulin therapy will be studied. The study population will have a large range of duration of diabetes and glycemic control.

6.2 Investigational Devices

The investigational devices used in this study will be described in this section. Instructions for intended use, including indications, contraindications, and precautions of the components used in this study, are provided in their respective user guide(s).

6.2.1 Insulin capture devices and associated apps

6.2.1.1 InPen Basal smart cap

The InPen Basal smart cap , also referred to as InCap, is a reusable electronic pen injector cap for single-patient use by people with diabetes. The Cap is compatible with Levemir®, Tresiba®, Lantus®, Basaglar®, and Toujeo® prefilled pens. In this study, the smart cap should be used under the supervision of an adult caregiver or by a patient age 7 and older for the tracking of long-acting insulin doses.

6.2.1.2 InPen Diabetes Management App, Version 6.0.0

The InPen app uses data from a user's InPen smart insulin pen system or InPen Basal smart cap to keep track of the user's data and helps the user make decisions. It automatically records insulin doses, tracks active insulin, recommends mealtime and correction doses, shares therapy data with the user's doctor or caregiver. The information collected by the InPen Diabetes Management app is stored on the Companion Medical data cloud and will be sent to the Nutrino data servers.

Medtronic Business Restricted

